# **Targeted Transcutaneous Spinal Cord Stimulation to Restore Autonomic Cardiovascular Health in Individuals with Spinal Cord Injury**

## **Abstract:**

Recent evidence indicates that increased arterial stiffness is an independent predictor of cardiovascular disease risk, which may contribute to the heightened cardiovascular morbidity and mortality in the spinal cord injury (SCI), compared to general, population. Increased reliance on the renin-angiotensin-aldosterone system (RAAS) is believed to mitigate orthostatic falls in blood pressure (BP) and reduce the severity of symptoms reporting; however, findings in the general population link the RAAS with vascular restructuring and remodeling. Therefore, clinical intervention to stabilize and normalize BP should be a priority in hypotensive individuals with SCI. Advances in methods of neuromodulation of the spinal processes offer a non-pharmacologic approach to restore endogenous autonomic cardiovascular control and improve orthostatic BP control. Based on our present understanding of the somatovisceral integration within the spinal cord, it is plausible that transcutaneous spinal cord stimulation (TSCS) can be targeted to excite and modulate appropriate spinal autonomic circuitry to rapidly normalize orthostatic BP; however, electrode placement and stimulation parameter mapping is needed to optimize orthostatic BP control. Therefore, our primary aim is to identify an individualized map using noninvasive TSCS of the spinal autonomic circuitry that results in an increase of seated BP. Our secondary aim is to compare BP, cerebral blood flow velocity (CBFv), plasma concentrations of norepinephrine, renin and aldosterone during a head-up tilt with and without optimal TSCS. Participants will go through a screening process to determine if participant experiences orthostatic hypotension. 12 participants who are cleared, will go through multiple mapping sessions to find out the most appropriate electrode placement to increase BP and then will perform an orthostatic provocation on a tilt table during stimulation to determine differences with stim and without.

**Objective:** To identify an individualized map of the spinal autonomic circuitry that results in an increase of seated BP using noninvasive TSCS.

## **Hypotheses:**

1. We hypothesize that electrode placement at the lower thoracic (T7/8) and 50 mA current will be the optimal parameters to increase cardiovascular function.
2. We hypothesize that seated systolic BP will significantly increase following optimal TSCS.

## **Review of Literature:**

Approximately 17,700 new cases of spinal cord injury (SCI) occur in the United States each year (1) and the Veterans Affairs (VA) provides care for approximately 26% of Americans with SCI, making it the single largest network of care for persons with SCI (2). The health care costs for Veterans with SCI are 6.5 times greater than the average veteran (2), and although improvements in post-injury care have contributed to extended life expectancies in the SCI population, longevity remains below the general population, due, in part, to an increased incidence of cardiovascular disease (CVD), which is a leading cause of mortality in individuals with chronic SCI (3). In 2013, a study completed retrospectively in 147 Veterans with SCI, demonstrated that those who survived the initial two years post-injury, are at increased risk of pre-mature coronary artery disease compared to the general population (4). Evidence is in agreement that morbidity due to CVD occurs at an earlier age in the SCI compared to the general population (4, 5) and we have reported that arterial stiffness may be an early sign of disease risk (4, 6).

Cardiovascular dysfunction following SCI stems in part from impaired autonomic nervous system control of hemodynamic reflexes that maintain homeostasis during the activities of daily living

(7). Sympathetic control of the upper extremity vasculature and the heart arises from T1-T5, whereas the splanchnic bed, which holds a majority of blood volume, and the lower extremity vasculature receive sympathetic input from T5-L2 (8). Parasympathetic innervation of the heart remains intact; however the synergistic function of both systems is disrupted causing segmental (lesion level) differences in sympathetic vascular control. In particular, diminished sympathetic cardiovascular control in individuals with lesions above T6 results in blood pressure (BP) instability which manifests as persistent hypotension, orthostatic hypotension and autonomic dysreflexia (8, 9). Importantly, restoration of autonomic dysfunction has been ranked as a higher priority than regaining the ability to walk in individuals with chronic SCI (10, 11). We demonstrated that ~25% of Veterans with SCI met the World Health Organization definition of hypotension (systolic BP  $\leq$  110 mmHg in males and  $\leq$  100 mmHg in females) (13), but less than 1% were diagnosed or treated (14). Additionally, our lab has reported evidence of BP instability, defined as fluctuation in systolic BP of more than 20 mmHg above or below average BP, in persons with SCI regardless of the level of injury (12), which has been linked to impaired sympathetic nervous system function and altered plasma catecholamine responses (15) to daily shifts in orthostatic gradients (16).

A common clinical problem affecting quality of life in the SCI population is orthostatic hypotension. According to a Consensus statement from the American Autonomic Society and American Academy of Neurology, orthostatic hypotension is defined as a decrease in systolic BP of  $\geq$  20 mmHg and/or a fall in diastolic BP of  $\geq$  10 mmHg, with or without symptoms (17). The prevalence of orthostatic hypotension is increased in individuals with cervical compared to individuals with thoracic lesions, irrespective of the completeness of injury (18), and orthostatic provocations during physical therapy in newly injured patients have been shown to decrease BP in 74% of individuals with SCI, which had a negative impact in rehabilitative outcomes (19). Interestingly, decreased plasma norepinephrine (NE) has been noted in individuals with cervical lesions in the seated position when compared to individuals with thoracic injuries and uninjured controls (20, 21), and change in plasma NE in response to an orthostatic challenge was blunted in individuals with cervical lesions compared to controls (6, 22). Additionally, lower levels of NE have been found to be associated with an increased incidence of orthostatic hypotension in persons with cervical SCI (23). On the other hand, individuals with lesions below the cervical spine have normal to high levels of plasma NE concentrations (6, 20, 21) and, as a result, are less prone to hypotension and orthostatic hypotension (22). In the absence of an integral sympathetic nervous system response to orthostasis, it is postulated that individuals with cervical injury rely more heavily on the renin-angiotensin-aldosterone system (RAAS) during postural challenges (6, 12, 24, 25).

The RAAS controls long-term BP through a cascade of hormones released into the plasma in response to a drop in BP or blood volume (26), and evidence in the general population links activation of the RAAS with undesirable vascular restructuring and remodeling (27, 28). Hyperactivity of RAAS causes an increase in oxidative stress, which leads to the formation of reactive oxygen species that has been shown to affect cell signaling and induce inflammation, vascular fibrosis and calcification (27). Furthermore, angiotensin II (ANG II), a potent vasoactive peptide, acts on the endothelium, to stimulate mitochondrial protein kinase C and ATP-dependent potassium channel opening, promoting further reactive oxidative stress (29). Plasma renin was shown to increase more significantly in individuals with cervical injuries during a head-up tilt maneuver as compared to individuals with thoracic injuries and uninjured controls (23, 30). Plasma renin stimulates the release of ANG II, which increases the production of aldosterone (10), and changes in plasma renin, in most situations, correlate with changes in serum aldosterone (31). Overuse of the RAAS for maintenance of BP homeostasis during orthostatic challenges may predispose individuals with SCI to premature vascular aging as has been reported in the general population (32).

Premature vascular aging has been proposed in response to structural changes that include degeneration of elastin, increases in collagen and thickening of the arterial walls, which can be estimated non-invasively by pulse wave velocity (28). As a vessel stiffens, the velocity of blood flow increases, and the reflected pressure wave form reaches the heart during systole rather than during diastole, amplifying systolic pressure and cardiac afterload (33). A number of studies have shown that

carotid-femoral pulse wave velocity, a direct measure of arterial stiffness and the “gold-standard”, is associated with higher CVD risk (34, 35) and is recognized as an independent predictor of disease risk in the general population (36). A 1 m/s increase in pulse wave velocity corresponds to a 15% increase in total cardiovascular events and mortality in the general population (36) and an increase in pulse wave velocity of 2-3 m/s is reported in the SCI population (6, 12, 33, 37, 38-40).

Increases in pulse wave velocity have been reported in otherwise young, healthy individuals with SCI (6, 12, 13, 19, 42-44). We reported that individuals with SCI with more severe and more frequent orthostatic hypotension are predisposed to significant increases in arterial stiffness as compared to individuals with SCI who do not experience orthostatic hypotension (4, 33). In fact, we reported an inverse relationship between seated systolic BP and arterial stiffness in individuals with SCI (4). To expand on this finding, we investigated the relationship between BP and hormonal responses to an orthostatic maneuver and demonstrated significantly lower plasma NE and significantly increased change in plasma renin during an orthostatic provocation in individuals with cervical SCI as compared to individuals with thoracic SCI and control groups. (6). Further, we found that the relationship between pulse wave velocity and orthostatic changes in plasma renin was significant among the groups, particularly in those with cervical SCI (6). These data suggest that maintaining orthostatic BP may reduce dependency on RAAS and lower CVD risk.

Numerous experimental and clinical studies have documented reversal of detrimental vascular remodeling following RAAS blockade with either an angiotensin converting enzyme inhibitor (ACEi) or ANG II receptor blockers. In the landmark Heart Outcomes Prevention Evaluation trial – hypertensive participants randomized to the ACEi Ramipril (10mg) for 5-years had a 22% lower relative risk of cardiovascular death, stroke and myocardial infarction as compared to hypertensive participants randomized placebo (41). However, these pharmacological options are contraindicated in hypotensive individuals with cervical SCI. In fact, we demonstrated that the use of anti-hypotensive i.e., hypertensive, medications, increased mean BP and reduced active plasma renin levels and serum aldosterone during a 45° head-up tilt maneuver in individuals with cervical level injuries (42). We recently reported increased BP instability after administration of a single dose of midodrine (10mg) in hypotensive individuals with SCI (43). These data suggest that maintaining orthostatic BP may reduce dependency on RAAS and lower CVD risk, but available clinical options are limited and perhaps contraindicated for wide-spread use in the SCI population. Therefore, alternate methods of stabilizing orthostatic BP within a normotensive range should be explored for use in the SCI population.

Mounting evidence supports the targeted use of electrical stimulation of the spinal cord to modulate autonomic nervous system circuitry and promote restoration of orthostatic BP control (44-47). To date, there is only one recent paper describing the effects of non-invasive transcutaneous spinal cord stimulation (TSCS) to increase BP during an orthostatic provocation. The TSCS parameters included electrode placement at the thoracic-7/8 vertebral level, using 10-70 mA current at 30 Hz, with monophasic, 1-ms pulses and the results demonstrated increases in orthostatic BP, improved cardiac contractility, and increased CBFv during active stimulation in 5 individuals with motor complete SCI (48). However, the investigators used TSCS at only one electrode placement site, and did not provide rationale for the electrode placement site, the frequency or pulse width chosen (48). The authors noted quiet electromyography (EMG) recordings of the lower-limb during stimulation, and conclude that the BP response were not attributed to the skeletal muscle pump action (48). The increase in orthostatic BP were therefore ascribed to excitation of sympathetic pre-ganglionic neurons leading to vasoconstriction and they conclude that TSCS may be a viable therapy for restoring autonomic cardiovascular control after SCI (48). However, we need to understand the effects of varied electrode placement site, and stimulation parameters (Hz, mA, pulse width) on BP and autonomic function before wide spread utility of TSCS can be recommended for clinical intervention.

[figure not shown]
### **Significance of the Research:**

Although life expectancies have improved in the SCI population, longevity remains below the general population, due to an increased incidence of CVD, which is a leading cause of mortality in individuals with chronic SCI. Autonomic nervous system dysfunction and BP instability contribute to the increased CVD risk in the SCI population; however, because a majority of individuals with SCI remain asymptomatic the diagnosis and treatment of BP instability is not a clinical priority. This is due, in part, to the lack of safe and effective interventions, even though mounting evidence strongly supports adverse effects of BP instability on the cerebral circulation, cognitive function, and quality of life. Identifying individualized TSCS parameters that safely and effectively increase and stabilize BP in hypotensive veterans with SCI will provide the foundational evidence to support eventual wide-spread clinical utility throughout the VA healthcare system. It is anticipated that these data will begin to establish a standard methodology for TSCS mapping of spinal autonomic circuits to promote restoration of orthostatic BP, which will be used in my CDA-2 application to investigate the enduring effects of TSCS as a viable treatment option to improve participation in daily activities, independence and quality of life for veterans with and other immobilizing conditions.

## Research Design and Methods

### Study Participants

**Study Participants:** It is our goal to recruit 12 eligible hypotensive individuals with injuries T6 and above. We anticipate recruitment of

4-5 eligible individuals each year of the project. Individuals with SCI will be recruited from the Northern New Jersey SCI Model System database via study solicitation flyer distribution at support groups and inpatient and outpatient treatment facilities.

### Inclusion Criteria:

- Between the ages of 21-70 years old;
- Individuals with traumatic spinal cord injuries at or above T6;
- Duration of injury is more than 1 year;
- Non-ambulatory;
- American Spinal Injury Association Scale A, B or C;
- Able to provide consent;
- Non-ventilator;
- Hypotensive (Males: systolic blood pressure less than 110 mmHg and/or diastolic blood pressure less than 70 mmHg; Females: systolic blood pressure less than 100 mmHg and/or diastolic blood pressure less than 70 mmHg).
- Orthostatic hypotensive (decrease in systolic blood pressure of at least 20 mmHg and/or decrease in diastolic blood pressure of at least 10 mmHg when moving from supine to upright position) (will be determined in the screening process).

### Exclusion Criteria:

- Acute illness or infection;
- Current smokers within 1 year of study;
- Documented history of controlled or uncontrolled diabetes, any other neurological condition other than a spinal cord injury (multiple sclerosis and Parkinson's disease);
- Cardiovascular disease (coronary artery disease, congestive heart failure, peripheral artery disease, stroke);
- Present or history of thrombosis in the last 12 months;
- Severe contractures.

### Methods & Procedures:

We aim to compare stimulation parameters (frequency and amplitude, 1-ms pulses) using a monophasic waveform for different spinal segment sites to modulate BP. Sites for stimulation during a series of seated experiments will include 1) T 7/8; 2) T 9/10; 3) T11/12; and 4) L1/2, while beat-to-beat seated BP is continuously monitored and recorded in hypotensive individuals with SCI.

This study will take approximately 7-study visits, between 1-3 hours, per subject. Participants will be asked to arrive between 8:00 am and noon at the James J Peters VA Medical Center (JJP VAMC), after a normal breakfast and a good night sleep. The participants will be asked to not drink alcohol or caffeine 12 hours prior to their visit and there will be at least 3 days between study visits.

Approach: We will compare the electrode placement sites and amplitude during seated rest to modulate BP. We anticipate that BP responses will vary among the participants regarding the location of the electrode placement site and signal amplitude. Participants will visit the laboratory 8 times: visit 1): informed consent and medical intake to determine eligibility for enrollment in the study. Visits 2-8: amplitude (mA) mapping sessions at each electrode placement site (randomized), with continuous beat-to-beat BP monitoring at the finger arteriole and at 1-minute intervals at the brachial artery.

In-person Interview, Consent Process and Eligibility determination and Orthostatic challenge without stimulation– Visit 1: Paperwork including consents and medical history will be conducted by the investigator for each participant. Participant eligibility will be determined by inclusion/exclusion criteria listed in the Human Subjects documentation. Cardiovascular systemic hemodynamics (heart rate and BP) will be measured in the seated position for 5 minutes. The participant will then lie down in the supine position for 10 minutes prior to collecting pulse wave velocity at the carotid and femoral artery. A blood sample of renin, aldosterone and NE will be drawn and continuous beat-to-beat heart rate, BP and CBFv will be recorded for 5 minutes. Participants will then be secured to a tilt table and will be tilted to 30°, 45° and 60° for 10 minutes at each angle with continuous beat-to-beat monitoring of the systemic hemodynamics. A second blood draw of renin, aldosterone and NE will be drawn at the end of 10 minutes at 60° tilt (**Table 2**). Participants will be deemed eligible for the TSCS mapping if their BP response to the head-up tilt maneuver meets the definition of orthostatic hypotension. A six-item validated orthostatic hypotension questionnaire will be used during the orthostatic tilt visits to report associated symptoms (54) (**Appendix**). Participants will undergo response to stimulation prior to entry to study and will be monitored for suitability to study protocol by [name] prior to stimulation.

Amplitude Parameter Mapping Visits 2-8: Before TSCS, electrodes will be placed on the vertebral midline at the spinous process (T7/8, T9/10, T11/12, L1/2), and the active site will be randomized. Each visit, we will complete one electrode placement site. Amplitude ramping will start at 10mA, with 10mA increments (pulse width, 1ms, frequency 30 Hz as shown (13)). Continuous real-time BP and heart rate will be measured for 5-minutes, before, during and after stimulation. During ramping, amplitude will stop increasing when SBP reaches optimal SBP between 110-120 mmHg (100-120 mmHg females) or reaches 100 mA with no SBP response (see below TSCS decision Tree). Amplitude will be decreased in 10 mA decrements in stimulation. BP will be continuously recorded during the rest period. Bilateral muscle activation (rectus femoris, medial hamstring, and gastrocnemius) will be monitored during all experiments to determine if skeletal muscle contractions are contributing to increases in BP. Additionally, signs and symptoms of autonomic dysreflexia will be monitored during TSCS testing in visits 3-6 by a questionnaire (**Appendix**). After every incremental increase of amplitude, investigator will ask participant if he/she is experiencing any symptoms. Maximum ramping amplitude will be 100 mA and testing will be halted if participant experiences any discomfort during testing. Based on preliminary work, regulation of neuromodulation of BP will occur at stimulation levels less than 100mA.

Participants will be notified by investigator if any of the findings from this study will affect the participants' health or welfare.

- Cardiovascular Assessments: While the subject is seated 3 ECG electrodes will be affixed to the chest and abdomen for continuous monitoring of HR and respiration rate (RR). Brachial BP will be monitored at 1 minute intervals using a standard adult BP cuff placed at the right upper arm, and beat-to-beat finger arteriolar BP will be continuously monitored from the right

middle finger throughout testing. Mean arterial pressure (mmHg) will be calculated from brachial BP using the formula: [systolic BP + (2\* diastolic BP)]/3. Beat-to-beat HR, RR and BP data will be viewed in real-time and stored for subsequent analysis using customized programs created with LabView graphical software.

- Transcutaneous spinal cord stimulation: Digitimer DS7A will be used to provide constant current voltage of electrical activity during the mapping and final orthostatic challenge. TSCS electrodes at different sites on the spinal process (T7/8, T9/10, T11/12, L1/2) and various amplitudes and frequencies will be assessed to determine the optimal site to increase blood pressure and decrease symptoms of orthostatic hypotension.

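### Sites are compared across days, but a participant's start time and interval from breakfast are free to vary and the model has no visit term

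*Protocol*

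**What the plan says.** The Methods & Procedures section of the protocol sets these visit-day conditions:

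- Arrival: "Participants will be asked to arrive between 8:00 am and noon".
- Preparation: "after a normal breakfast and a good night sleep". Participants are also asked to "not drink alcohol or caffeine 12 hours prior to their visit and there will be at least 3 days between study visits".
- Sites: "Each visit, we will complete one electrode placement site". The order is randomised: "Visits 2-8: amplitude (mA) mapping sessions at each electrode placement site (randomized").
- Same-visit baseline: BP and heart rate are recorded for 5 minutes before stimulation as well as during and after it.
- Stopping: the ramp ends when systolic BP enters an absolute range, 110-120 mmHg in males and 100-120 mmHg in females (mapping paragraph and BP decision tree).

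The number of visits is not settled. Methods & Procedures says "This study will take approximately 7-study visits" and then describes eight; Study Compensation pays for nine. Mapping is assigned to visits 2-8, which is seven visits for four sites, while the dysreflexia questionnaire is tied to visits 3-6.

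The SAP takes systolic BP as the primary outcome, with participant as a random effect and stimulation characteristics, including site and current, as fixed effects. It names no visit or day term and no visit-baseline covariate. Baseline is used only for Cohen's d at each participant's optimal parameters. The SAP claims 95% power for mean differences below 2 mmHg, on the strength of the repeated readings per participant.

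**The concern.** A participant could be tested at one site early in the morning soon after eating, and at another site near noon several hours after eating. Nothing in the protocol keeps these conditions alike within a participant or has the meal interval recorded. Any effect on that day's BP is carried by every reading of the visit, and so by the site tested at that visit.

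Two things are at stake. The first is the group comparison of sites: a model that treats readings from one day as independent, given the participant, will report a site contrast as more precise than it is. The second is the study's main product, an individual map. If a site has only one visit, that day's shift in BP level cannot be told apart from the site's effect on BP level.

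Starting BP also affects how far the ramp goes, because the target is absolute.

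**Working it through.** **Inputs from the documents.** 12 participants; four sites; one site per visit; at least 3 days between visits; 95% power below 2 mmHg at 95% confidence (taken as two-sided 0.05). Eight visits have seven gaps, so they span at least 7 × 3 = 21 days.

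**Inputs the documents do not give.** Visit-to-visit SD, reading SD and number of readings. All values for these below are assumptions.

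**The plan's own figure.** It cannot be reproduced without those SDs. What it requires can be worked out. For a two-site contrast within participants the participant effect cancels, so

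SE = SD_eff × √(2/12), with SD_eff² = SD_visit² + SD_reading²/m

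for m readings per visit and one visit per site. At 95% power (normal approximation) the difference must equal (1.960 + 1.645) × SE = 3.605 × SE. For 2 mmHg, SE ≤ 2/3.605 = 0.555, so SD_eff ≤ 0.555/0.408 = 1.36 mmHg.

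With SD_visit = 0 this can be met: reading SD 5 and 20 readings give 99% power, and reading SD 8 with 30 readings gives 92%. With one visit per site, a visit-to-visit SD above 1.36 mmHg rules it out, however many readings are taken within the visit.

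**Contribution of visit-to-visit variation.** SD_visit × √(2/12):

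| Assumed SD_visit (mmHg) | Contribution to SE (mmHg) |
|---|---|
| 3 | 3 × 0.408 = 1.22 |
| 5 | 5 × 0.408 = 2.04 |
| 8 | 8 × 0.408 = 3.27 |

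These combine in quadrature with other error. Example with reading SD 8 and 10 readings: SD_reading²/m = 64/10 = 6.4. With SD_visit = 0, SE = √6.4 × 0.408 = 1.03 and the detectable difference is 3.7 mmHg. With SD_visit = 5, SE = √(25 + 6.4) × 0.408 = 2.29 and it is 8.3 mmHg.

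**If sites are repeated.** If all seven visits were mapping visits, there would be 7/4 = 1.75 per site on average. Each contribution is divided by √1.75 = 1.32, giving 0.93, 1.54 and 2.47 mmHg.

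**False precision.** With no true site difference, 12 participants, one visit per site, 10 readings and reading SD 8, a simulation of 4,000 trials per setting gave these error rates for the overall site test when only participant effects are modelled:

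| SD_visit (mmHg) | Type I error |
|---|---|
| 0 | 4.6% |
| 2 | 17% |
| 3 | 30% |
| 5 | 56% |
| 8 | 75% |

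Analysing change from a five-reading same-visit baseline removed the dependence on SD_visit, but the error stayed at 38-39%, because all readings of a visit then share one baseline error. A visit-level term is needed in either case.

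**Starting BP and the ramp.** Take a man at 98 mmHg on one day and 106 on another. On the target range alone he needs 110 − 98 = 12 or 110 − 106 = 4 mmHg. If a 10 mmHg rise is also required, 98 + 10 = 108 is short of the range and the ramp continues, while 106 + 10 = 116 is inside it. Subtracting baseline afterwards does not change the current at which the ramp stopped.

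**The case against.** The case for the plan is substantial. Visits are confined to mornings, after breakfast and sleep and without alcohol or caffeine. BP is recorded before stimulation at every mapping visit, the decision tree judges response against baseline, and the model's current range includes 0 mA. A shift that lasts the whole visit is also in that visit's baseline.

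This stands in part. The baseline removes an additive shift only if the site comparison uses it. The SAP reserves it for Cohen's d and names no site-by-current interaction through which the 0 mA readings would do that work.

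Four stronger readings are tempting, and the documents do not support them:

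- *Each site is tested exactly once.* One site per visit does not mean one visit per site. Seven mapping visits for four sites leave room for repeats, although the questionnaire at visits 3-6 would fit one each.
- *Day shifts bias the study towards a site.* The site is randomised, so at group level they add noise and overstate precision, without favouring a site.
- *The protocol itself shows large visit-to-visit variation.* In the Review of Literature, "fluctuation in systolic BP of more than 20 mmHg above or below average BP" is the definition of BP instability. It is not a visit-to-visit SD and is not linked to clock time or meals.
- *The missing illness check is a design error.* "Acute illness or infection" is an exclusion, eligibility is determined at visit 1, and no later re-check is stated. But the protocol also provides for monitoring of suitability, symptom questions during the ramp and a physician present at testing, and it refers to other documentation for the criteria. The most that follows is a request for clarification.

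**Conclusion.** The concern holds in a limited form. Sites are compared across days, two controllable sources of day-to-day BP variation are left free within a participant, and the planned model has no term for the day. The result is extra noise and understated standard errors at group level. For an individual's optimal site, it is confounding to the extent that a site has a single visit.

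The size is illustrative only: 1.2 to 3.3 mmHg in the standard error of a two-site contrast for an assumed visit-to-visit SD of 3 to 8 mmHg, with 12 participants and one visit per site. Clock time and meal interval account for an unknown share of that SD. If scheduling removes a share f of the visit variance, the contribution shrinks only by the factor √(1 − f). This is a cheap improvement and does not show that the trial cannot answer its question.

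**What to change.** 1. **Protocol, Methods & Procedures.** Schedule all of a participant's mapping visits at about the same clock time (for example within 30 minutes) inside the existing 8:00-noon window, at a similar, recorded interval from a similar breakfast.
2. **SAP.** Add a participant-by-visit random effect. It covers the day variation that scheduling cannot remove and corrects the group-level standard errors. With one visit per site it cannot separate a day shift from a real individual site preference, so the first change is still needed for the maps. Rerun the power simulation with this term and state the SDs and number of readings used.
3. **Visit counts.** Reconcile about seven, eight and nine, and state how many visits each site receives.
4. **Clarification only.** Reconcile Exclusion Criteria with the mapping-visit text on whether the acute-illness exclusion applies at mapping visits.

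The cost is some scheduling burden for non-ambulatory participants, one recorded time per visit and one extra model term. The rerun power figure may be less favourable than the one now stated.
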